## Part B

A single interim analysis is planned after at least 50% of patients enrolled on Part B have completed Day 29 assessments. The interim analysis allows for stopping due to efficacy, to allow for possible accelerated development of ensovibep. A final analysis for Part B will be done once all patients in Phase 3 complete the study, i.e. Day 91 of follow up.

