## Part B

There is one interim analysis after at least 50% of patients complete Day 29 and one final analysis after at least 1717 patients have completed Day 91. The interim analysis permits early stopping due to efficacy controlling overall type I error rate. The interim analysis upper stopping bound in Z scale is 2.963 (corresponding to alpha is 0.03).

Further details will be provided in a separate Interim Analysis SAP.

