## Part B

Assuming the proportion of patients achieving the composite endpoint (of hospitalizations [ $\geq$  24 hours of acute care] and/or emergency room visits, related to COVID-19, or death from any cause) up to Day 29 is 6.5% based on [Gottlieb et al \(2021\)](#) in the placebo group and 50% reduction with to 3.25%, a sample size of 1717 patients 1:1 randomized to two treatment groups provides at least 90% power that the primary analysis will be statistically significant using a two-sided log rank test with 5% significance level assuming that the survival rates are exponential. These results assume that the group sequential design has one interim analysis for stopping the trial early for efficacy after 50% of patients complete Day 29 visit (two total analysis including final analysis) and the O'Brien-Fleming spending function is used to determine the efficacy test boundary.

Given possible enrichment for more severe COVID-19 cases, a range of operating characteristics were evaluated and presented in [Table 12-2](#).

Sample size calculations are performed in nQuery 8.4.1.0.

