1.1 Study design

This is a randomized, double-blind, placebo-controlled, multicenter study of ensovibep (MP0420) in ambulatory patients with symptomatic COVID-19. The study has two parts: A Phase 2 dose-ranging study to select the best dose over the therapeutic range (Part A) and a confirmatory Phase 3 safety and efficacy study of the dose determined in Part A (Part B).

Screening will be used to determine eligibility. Randomization and treatment will be conducted on Day 1 (screening can optionally be done up to 3 days earlier, or also at Day 1) and with a study duration for individual patients of 91 ± 7 days for both Parts.

Part A

[figure not shown]
This dose-ranging part of the study will include approximately 400 randomized patients in four arms (3 active arms and one placebo arm), randomized 1:1:1:1 (see also [Figure 1-1](#)) to receive ensovibep (75 mg, 225 mg, or 600 mg) or placebo, administered as a single i.v. infusion over

60 minutes, and stratified by risk for COVID-19 disease progression (“high-risk”, “not at high-risk”)..

Part B

Recruitment will begin in Part B once the best safe and efficacious dose has been selected from Part A based on Day 29 data analysis. Part B will include at least 1717 patients randomized 1:1 (see also [Figure 1-1](#)) to either the selected dose of ensovibep or placebo, administered as i.v. infusion over 60 minutes. An interim analysis for early efficacy will be conducted when approximately 50% of patients have completed the Day 29 assessments. Patients will be stratified by risk for COVID-19 disease progression (“high-risk patients” versus “not at high-risk patients”).

Figure 1-1 Study design

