2.14 Interim analysis

Part A

No interim analysis will be performed for the efficacy evaluation. Analysis of primary endpoint will be carried out when all patients have completed the Day 29 visit (or withdrawn prematurely) and have viral load data up to Day 8. Final analyses of part A will occur when all patients have completed Day 91 visit (or withdrawn prematurely). However, analyses of primary endpoint will not be repeated.

For the Part A primary analysis a cut-off date will be applied. All available data up to the cut-off date will be included in the analysis. The cut-off date is defined as the date when the last patient completed Day 29 visit or discontinued prematurely.

At time of primary analyses not all data up to the cut-off date will be available. Incomplete data are expected for

- Viral load data beyond Day 8.
- SARS-CoV-2 IgM / IgG antibodies data for Day 91
- Anti-SARS-CoV-2 neutralizing antibody test data – no data will be available

[REDACTED]

- PK data beyond Day 8

[REDACTED]

- Serum biomarker data – any visit

If not stated otherwise in the respective section, all analyses will be included in the Part A primary analyses. Analyses will include all available data.

Part B

There will be one interim analysis after 50% of patients complete Day 29 and one final analysis after at least 1717 patients have completed Day 91. The interim analysis permits early stopping due to efficacy controlling overall type I error rate. The interim analysis upper stopping bound in Z scale is 2.963 (corresponding to alpha is 0.03).

3 Sample size calculation

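### The Part B interim bound is fixed at Z=2.963, which the stated O'Brien-Fleming spending function gives only at exactly half the information, while the trigger counts patients and is worded three ways

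*Protocol*

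**What the plan says.** Protocol 12.7, Part B, fixes the bound: "The interim analysis upper stopping bound in Z scale is 2.963". The same sentence equates it with an alpha of 0.03. SAP 2.14 repeats both. Neither document ties the value to an information fraction, says it will be recomputed, or gives a final critical value.

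Protocol 12.8.1 (repeated in SAP 3.1) takes the bound from a rule instead: the O'Brien-Fleming "spending function is used to determine the efficacy test boundary". The design there assumes "stopping the trial early for efficacy after 50% of patients complete Day 29 visit (two total analysis including final analysis".

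The trigger varies:
- Protocol 12.7: "There is one interim analysis after at least 50% of patients complete Day 29 and one final analysis".
- Protocol 4.4: "A single interim analysis is planned after at least 50% of patients enrolled on Part B have completed Day 29 assessments".
- SAP 1.1: "An interim analysis for early efficacy will be conducted when approximately 50% of patients have completed the Day 29 assessments".
- SAP 2.14: "There will be one interim analysis after 50% of patients complete Day 29".

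Protocol 12.7 leaves further detail to a separate Interim Analysis SAP. SAP section 1 leaves Part B detail to an amendment before the first Part B patient.

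**The concern.** A spending function yields a bound only once the information at the look is known. Here the rule is named in one section and its value for a single time point is fixed in another. Two features make that time point doubtful. A minimum of 50% has no upper limit. And the trigger counts patients at Day 29, while the primary analysis in protocol 12.4.2 uses Kaplan-Meier estimates with Greenwood variance, to which patients short of Day 29 also contribute unless the data cut excludes them. Nothing in the documents excludes them.

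Protocol 4.4 says the look is there to permit stopping for efficacy and so speed development. A bound stricter than the spending rule allows weakens that single function and buys nothing useful in type I error. In the other direction, the protocol 4.4 wording, read literally as half of those enrolled so far, could bring the look before half the information, where 2.963 is too lenient.

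**Working it through.** **Inputs from the documents.** Two-sided 5% (one-sided 0.025), O'Brien-Fleming spending, two analyses, N=1717 randomized 1:1, event rates 6.5% and 3.25%, exponential survival, log-rank test, stated power 90.02% (protocol 12.8.1 and Table 12-2).

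**Reproducing 2.963.** One-sided alpha spent at information t is 2[1 − Φ(2.2414/√t)], where 2.2414 is the 1 − 0.0125 normal quantile. At t=0.50, 2.2414/√0.50 = 3.170 and the spend is 0.00153. The bound is therefore 2.963, as printed. The two-sided p-value for 2.963 is 0.003. A level of 0.03 would correspond to Z=2.170 (two-sided) or 1.881 (one-sided), so the printed 0.03 does not belong to this bound.

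**Reproducing the design.** The final bound c solves P(Z1 < 2.963, Z2 < c) = 0.975 with correlation √0.50, giving 1.969. The drift for 90% power is θ = 3.247. HR = ln(1 − 0.0325)/ln(1 − 0.065) = 0.4916. Events = 4θ²/(ln HR)² = 83.6, and 83.6/0.04875 gives N=1716 against the stated 1717. Power at 1717 is 90.02%, as stated.

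**Effect of a look away from t=0.50.** Chance of stopping at the interim = 1 − Φ(bound − θ√t). At t=0.60, θ√t = 2.515. The fixed bound gives 1 − Φ(0.448) = 33%; the recomputed bound gives 1 − Φ(0.154) = 44%. The type I column keeps 2.963 at the interim and 1.969 at the final.

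| t | Bound from spending function | Stop, fixed 2.963 | Stop, recomputed | One-sided type I, fixed |
|---|---|---|---|---|
| 0.45 | 3.144 | 22% | 17% | 0.0251 |
| 0.50 | 2.963 | 25% | 25% | 0.0250 |
| 0.52 | 2.897 | 27% | 29% | 0.0250 |
| 0.55 | 2.806 | 29% | 35% | 0.0249 |
| 0.60 | 2.669 | 33% | 44% | 0.0248 |
| 0.65 | 2.547 | 37% | 53% | 0.0247 |
| 0.70 | 2.438 | 40% | 61% | 0.0247 |

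Overall power with the fixed bounds is 90.0% throughout. With both bounds recomputed it is 89.9% at t=0.60 and 89.7% at t=0.70.

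**Where t might fall.** The documents give no accrual rate, so this step is an assumption: uniform accrual over T days, a look exactly when half of 1717 have reached Day 29, and partial follow-up counted. Then t = 0.5 + (28/T) × (mean share of 28-day events already seen in those still in follow-up). That mean is 0.50 for a constant hazard, and 0.769 if events come early (exponential with mean 7 days, truncated at 28).

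| T (days) | t, constant hazard | t, early events | Loss in chance of stopping (points) |
|---|---|---|---|
| 365 | 0.538 | 0.559 | 4.3 to 6.6 |
| 180 | 0.578 | 0.620 | 8.7 to 13.3 |
| 90 | 0.656 | 0.739 | 16.9 to 23.5 |

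**The case against.** A reader might infer that the trigger forces a late look and that the trial thereby gives up much of its chance to stop early. The documents do not support that. A minimum of 50% permits a later look without requiring one, and the sample size text and SAP 2.14 both say 50%. If the data cut were limited to Day 29 completers, information at the trigger would be about one half. With 2.963 kept, the chance of stopping rises as the look moves later, from 25% at t=0.50 to 40% at t=0.70, so nothing is lost against the design as planned. The loss exists only against what the spending function would allow. Losses of 16 points or more need t of about 0.65, hence fast accrual or a late cut. With 90-day accrual, 50% + 28/90 = 81% of patients are already enrolled at the look, so stopping then saves the least recruitment. All of this stands, and it limits the size of the point.

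It can also be said that the spending function is named, that the final bound is not fixed, and that recomputation is ordinary content for the promised Interim Analysis SAP. That is fair as far as it goes. But the protocol and SAP both print 2.963 without condition, so a later document that used another value would contradict them. The deferral does not settle the matter.

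**Conclusion.** The point holds as an inconsistency with a moderate cost. The plan names a spending rule but fixes its value at one information fraction, with a trigger that does not secure that fraction. If the look falls at t of 0.52 to 0.60, the chance of stopping early under the design effect is about 2 to 11 percentage points below what the rule allows. Larger losses depend on an accrual rate that the documents do not give. Validity is not at issue: one-sided type I error with the fixed bounds lies between 0.0246 and 0.0252 for t from 0.40 to 0.75, the small excess arising only before t=0.50, and overall power stays at about 90%. The mismatch between 2.963 and a level of 0.03 needs no assumption and should be corrected in any case.

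**What to change.** In protocol 12.7 and SAP 2.14:

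1. State that 2.963 (two-sided p 0.003) is the bound at an information fraction of 0.50, and remove the 0.03.
2. State that the interim and final critical values will be computed from the O'Brien-Fleming spending function, two-sided 5%, at the information fraction observed at the interim.
3. Name one information clock in advance, suited to a trial that ends on 1717 patients: for example, observed over projected final information from the Greenwood variance. Events over the planned 84 would mislead if event rates differ from 6.5% and 3.25%. At the 10% and 5% rates in Table 12-2 with N kept at 1717, half the patients give 858.5 × 0.075 = 64 events, which reads as 77% when information is about half the final total.
4. Use one trigger wording throughout, such as 859 of 1717 patients with Day 29 complete, and say whether patients short of Day 29 enter the interim data cut.

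This takes a few sentences, no patients and no extra alpha. The final critical value rises slightly with a later look, costing at most about 0.3 points of overall power for t up to 0.70. The Part B amendment to the SAP is a natural place for the detail, provided the protocol text is aligned with it.

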## 12.8 Sample size calculation

### 12.8.1 Primary endpoint(s)

## Part A

In Documentation for the EUA for emergency use of casirivimab and imdevimab, issued 21-Nov-2020, it is shown that the treatment effect in time-weighted change from baseline (Day 1) to Day 8 of log10 SARS-CoV-2 viral load in nasopharyngeal swabs was -0.36 for the overall population and -0.68 for the subgroup of patients with at least 107 copies at baseline and the estimated SD was between 1.0 and 1.2.

Assuming the published evidence to be predictive over 8 days, a sample size of at least 100 patients per treatment group, for a total of 400 patients, would have at least 80% power (minimum power over the considered candidate shapes) with a one-sided Type I error rate of 0.10 to detect a dose-response trend versus placebo using MCP-Mod to select the smallest dose for consideration in the decision to move into Part B.

The power calculations given the range of operating characteristics (treatment effect: -0.36, -0.68, and standard deviation: 1, 1.1, 1.2) were performed based on MCP-Mod in R (84) and are presented in Table 12-1.

**Table 12-1 Power for Part A given a range of operating characteristics given 400 patients, 100 patients in each arm and a one sided significance level of 10%**

Treatment Effect	Standard Deviation	Power (%)
	1	90.03
-0.36	1.1	85.25
	1.2	80.25

	1	99.98
-0.68	1.1	99.92
	1.2	99.73

## Part B

Assuming the proportion of patients achieving the composite endpoint (of hospitalizations [ $\geq$  24 hours of acute care] and/or emergency room visits, related to COVID-19, or death from any cause) up to Day 29 is 6.5% based on [Gottlieb et al \(2021\)](#) in the placebo group and 50% reduction with to 3.25%, a sample size of 1717 patients 1:1 randomized to two treatment groups provides at least 90% power that the primary analysis will be statistically significant using a two-sided log rank test with 5% significance level assuming that the survival rates are exponential. These results assume that the group sequential design has one interim analysis for stopping the trial early for efficacy after 50% of patients complete Day 29 visit (two total analysis including final analysis) and the O'Brien-Fleming spending function is used to determine the efficacy test boundary.

Given possible enrichment for more severe COVID-19 cases, a range of operating characteristics were evaluated and presented in [Table 12-2](#).

Sample size calculations are performed in nQuery 8.4.1.0.

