### 2.1.2 Part B

The primary clinical question is: what is the effect of ensovibep compared to placebo on reducing the percentage of patients requiring hospitalizations and/or emergency room visits related to COVID-19 or death from any cause up to Day 29 in ambulatory adult patients with newly symptomatic COVID-19? Hospitalization is defined as  $\geq 24$  hours of acute care, in a hospital or similar acute care facility instituted to address medical needs of those with severe COVID-19 during the COVID-19 pandemic.

The primary efficacy response is hospitalizations ( $\geq 24$  hours of acute care) and/or emergency room visits related to COVID-19 or death from any cause up to Day 29 and rationale for selection as a primary objective can be found in [Section 4.1](#).

The primary estimand definition is as follows:

1. **Population:** defined through appropriate inclusion/exclusion criteria to reflect the targeted population, ambulatory adult patients with newly symptomatic COVID-19 with onset of symptoms within 7 days prior to dosing and with a positive rapid antigen test on the day of dosing
2. **Treatment of interest:** the randomized treatment (ensovibep [dose selected from Part A] or placebo) added to concomitant symptomatic/preventive treatments, including symptomatic therapies (e.g., antipyretics/analgesics such as ibuprofen, paracetamol/acetaminophen, aspirin) and anticoagulants (e.g., heparin), used for mild-to-moderate COVID-19
3. **Endpoint:** the binary response of patients experiencing hospitalizations ( $\geq 24$  hours of acute care) and/or emergency room visits related to COVID-19 or death from any cause up to Day 29 (Yes/No)
4. **Handling of intercurrent event(s):** A treatment policy strategy will be used to handle (1) post-treatment initiation of all antivirals (including convalescent serum, antiviral antibodies, and antiviral small molecules), immunomodulating medications; and, (2) post-treatment increase in dose of immunosuppressive medications, for the treatment or management of COVID-19
5. **Summary measure:** difference in proportions of patients experiencing hospitalizations ( $\geq 24$  hours of acute care) and/or emergency room visits related to COVID-19 or death from any cause up to Day 29 of ensovibep (dose selected from Part A) compared to placebo

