## Part B

The primary objective of this Part is to demonstrate superiority of ensovibep, compared to placebo, in reducing the occurrence of hospitalizations ( $\geq 24$  hours of acute care) and/or emergency room visits related to COVID-19 or death from any cause up to Day 29.

The cumulative proportion of experiencing hospitalizations ( $\geq 24$  hours of acute care) and/or emergency room visits related to COVID-19 or death from any cause up to Day 29 will be estimated for each randomized group using Kaplan-Meier methods to take account of losses to follow-up.

The difference between randomized groups in the estimated log cumulative proportion will be calculated and the variance for this difference will be obtained using Greenwood's formula. Two-sided 95% CIs (adjusted for an interim analysis) and associated p-value for the test of no difference between groups will then be obtained.

The hazard ratios for these comparisons for the occurrence of hospitalizations ( $\geq 24$  hours of acute care) and/or emergency room visits related to COVID-19 or death from any cause and their corresponding 95% CIs will be computed using a stratified Cox proportional hazards regression model, stratified by baseline risk of progression to severe COVID-19 and/or hospitalization ("high risk" versus "not at high risk").

Time to hospitalizations ( $\geq 24$  hours of acute care) and/or emergency room visits related to COVID-19 or death from any cause will be presented graphically with a Kaplan-Meier plot.

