##### **Part B**

Simple event rate estimates (proportion of events) will be presented for the primary composite efficacy endpoint.

An alternative estimand may be considered with a composite strategy account for the intercurrent events of (1) post-treatment initiation of all antivirals (including convalescent serum, antiviral antibodies and antiviral small molecules), ambulatory oxygen, and immunomodulating or immunosuppressive medications; and, (2) post-treatment increase in dose of ambulatory oxygen, and immunomodulating or immunosuppressive medications, for the treatment or management of COVID-19. The primary endpoint will be considered a failure at the time of the intercurrent event.

The primary efficacy analysis may be repeated excluding patients who experienced a negative PCR COVID-19 test following a positive swab.

A tipping point analysis will be conducted to assess the impact of the missing data strategy in [Section 12.4.4](#).

Additional analyses to address sensitivity of assumptions may be performed including inverse probability of censoring modeling.

Further details on supplementary analyses can be found in the SAP.

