**Table 12-2 Power for Part B given a range of operating characteristics**

Total Sample Size	Placebo Event Rate (%)	Drug Event Rate (%)	Power (%)
1717	6.5	3.25	90.02
1588	7	3.5	90.01
1476	7.5	3.75	90.01
1380	8	4	90.04
1295	8.5	4.25	90.06
1217	9	4.5	90.03
1148	9.5	4.75	90.02
1086	10	5	90.02

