2.5 Analysis of the primary objective

Part A

The primary analysis in Part A is conducted on the data cut performed after the last enrolled Part A patient completes Day 29 visit or discontinues prematurely.

Part B

The primary analysis in Part B is conducted on the data cut performed after the last enrolled Part B patient completes Day 91 visit.

An outline of the protocol-specified analysis of Part B is provided in the SAP. Further details will be provided in a SAP amendment before FPFV of Part B.

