The cumulative proportion of experiencing hospitalizations (\geq 24 hours of acute care) and/or emergency room visits related to COVID 19 or death from any cause up to Day 29 will be estimated for each randomized group using Kaplan-Meier methods to take account of losses to follow-up.

The difference between randomized groups in the estimated log cumulative proportion will be calculated and the variance for this difference will be obtained using Greenwood's formula. Two-sided 95% confidence intervals (adjusted for an interim analysis) and associated p-value for the test of no difference between groups will then be obtained.

The hazard ratios for these comparisons for the occurrence of hospitalizations (\geq 24 hours of acute care) and/or emergency room visits related to COVID 19 or death from any cause and their corresponding 95% confidence intervals will be computed using a stratified Cox proportional hazards regression model, stratified by baseline risk of progression to severe COVID-19 and/or hospitalization ("high risk" vs. "not at high risk").

Time to hospitalizations (\geq 24 hours of acute care) and/or emergency room visits related to COVID 19 or death from any cause will be presented graphically with a Kaplan-Meier plot.

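### Part B's estimand, primary contrast and power statement name three different things: a difference in proportions, a log ratio and a log-rank test; the planned test has about 88% power, not at least 90%

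*Protocol*

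**What the plan says.** - **Estimand.** Protocol 2.1.2 and SAP 2.5.1 give the Part B summary measure as a "difference in proportions of patients experiencing hospitalizations" and the other components of the composite up to Day 29, drug compared with placebo.
- **Primary analysis.** Protocol 12.4.2 and SAP 2.5.2 estimate each arm's cumulative proportion by Kaplan-Meier. Then: "The difference between randomized groups in the estimated log cumulative proportion will be calculated", with a Greenwood variance. The interim-adjusted 95% interval and the p-value come from that contrast.
- **Other between-group estimate.** A hazard ratio, with its interval "computed using a stratified Cox proportional hazards regression model, stratified by baseline risk of progression to severe COVID-19". The SAP plans the same Cox model.
- **Supplementary.** Protocol 12.4.5: "Simple event rate estimates (proportion of events) will be presented for the primary composite efficacy endpoint". No between-group interval is mentioned there.
- **Sizing.** Protocol 12.8.1 and SAP 3.1 assume 6.5% against 3.25%, 1717 patients randomized 1:1, exponential survival and one O'Brien-Fleming efficacy look at 50%. They say this "provides at least 90% power that the primary analysis will be statistically significant using a two-sided log rank test with 5% significance level". Protocol Table 12-2 and SAP Table 3.1-2 list eight combinations of sample size and event rate, each with power between 90.01% and 90.06%.
- **What is still to come.** SAP 2.5 on Part B: "Further details will be provided in a SAP amendment before FPFV of Part B".

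**The concern.** There are two inconsistencies in the confirmatory part of the trial.

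First, the estimand asks for an absolute difference, while the primary contrast is a log ratio and the secondary estimate is a hazard ratio. The headline result would then carry no pre-specified interval for the quantity the estimand defines. A risk-difference interval could be built from the per-arm Kaplan-Meier estimates, but no estimator or interim adjustment is written down for it.

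Second, the power claim is attached to the primary analysis but names a test that the analysis sections do not contain. A reader cannot tell which test is primary, and the figure given need not apply to the one that will be run.

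**Working it through.** **Inputs.** N = 1717, 1:1; 6.5% and 3.25%; exponential survival (Protocol 12.8.1). Interim bound Z = 2.963 (Protocol 12.7), which is the O'Brien-Fleming spending value at half the information. The final bound, solved for an overall one-sided 0.025, is 1.9686. The documents state no dropout rate, so the main figures assume none.

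**Step 1: reproduce the plan's figure.**
- Hazard ratio = ln(0.9675)/ln(0.935) = 0.4916.
- Expected events = 858.5 × (0.065 + 0.0325) = 83.7.
- Schoenfeld drift = √(83.7/4) × |ln 0.4916| = 3.248.
- Probability of crossing 2.963 at half information or 1.9686 at the end = 90.02%, which is the printed value.
- The other seven rows of Table 12-2 reproduce within about 0.01 point. The documents do not name this formula; it is inferred from the match. Freedman's formula gives 87.6% and a pooled two-proportion formula 87.7%, so neither is the source.

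**Step 2: power of the planned test.** Without censoring, the Kaplan-Meier estimate is the observed proportion and Greenwood's variance is the binomial one. The statistic is

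Z = ln(p₀/p₁) / √[(1−p₀)/(n₀p₀) + (1−p₁)/(n₁p₁)].

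Exact enumeration of the binomial outcomes over both looks, with one-sided type I error at 6.5% in both arms:

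| Test at N = 1717 | Power | Type I error |
|---|---|---|
| Stated (Schoenfeld) | 90.02% | – |
| Planned log cumulative proportion, exact | 88.0–88.2% | 2.4% |
| Risk difference, exact | 88.5% | 2.5% |
| Log-rank, simulated (400,000 trials) | 88.5% | – |

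The small range for the planned test depends on whether the final bound is rounded to 1.969 and on which arm takes the odd patient. Over all eight rows the planned test has 88.0 to 88.2% and the log-rank test 88.4 to 88.6%.

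**Step 3: split the gap.** From 90.02% to the log-rank's 88.5% is about 1.5 points. That is optimism in the formula and would remain if log-rank were the planned test. From log-rank to the planned test, compared in the same simulated trials, is 0.32 points at 1717 and 0.32 to 0.53 over the rows.

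**Step 4: sensitivity.**
- Full Kaplan-Meier/Greenwood simulation of the planned test with assumed dropout of 0, 3 and 5% by Day 29 gives 87.9, 87.7 and 87.3% (simulation standard error 0.16).
- At 1717, the planned test has about 85% power for 6% against 3%, and 90.4 to 90.5% for 7% against 3.5%.
- For 90% at the planned rates with no dropout, exact enumeration gives 89.98% at 1824 patients and 90.02% at 1826.

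**Step 5: what the scale mismatch looks like.** Take 56/859 on placebo and 28/858 on drug, the planned rates, with unadjusted 95% intervals.
- The plan's contrast: ratio 0.50. SE of the log ratio = √[(1−0.0652)/56 + (1−0.0326)/28] = 0.226, so the interval is 0.32 to 0.78.
- The estimand's quantity: −3.3 percentage points. SE = √[0.0652×0.9348/859 + 0.0326×0.9674/858] = 0.0104, so the interval is −5.3 to −1.2 points. Neither document plans this interval.

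**The case against.** The power half can fairly be called a reproducible figure rather than a mistake. The protocol states a test, a survival model, a spending function and its software, and the figure follows from a standard formula. The gap is about two points, most of it approximation error. With efficacy held at 50%, a placebo rate of 6.9% instead of 6.5% would bring the planned test to about 90%, and that is well inside the uncertainty of the assumed rate. This stands, and it limits the weight of the power shortfall. It does not rescue the wording, since neither the named test nor the planned one delivers at least 90% at the stated rates.

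On the scale, the SAP gives only an outline for Part B and promises detail later. A risk difference needs no new data, and both scales test the same null, so no decision about superiority changes. All of this is true. But the primary contrast is already fixed in Protocol 12.4.2 and SAP 2.5.2, and the conflicting estimand, contrast and power statements also sit in the protocol. A SAP amendment alone would leave them standing.

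It can also be objected that restating 88% quietly gives up a 90% target. That is right: the sponsor should make that choice openly.

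**Conclusion.** The concern holds. The estimand, the primary contrast and the power statement do not refer to the same quantity or the same test, and no planned between-group interval is on the estimand's scale. Reading the log cumulative proportion as the log event-free proportion does not help, because that also back-transforms to a ratio.

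At 1717 patients and 6.5% against 3.25%, the planned test has about 88% power against a stated 90.02%. This assumes exponential event times, the stated interim bound and no dropout; dropout lowers it slightly. The printed figure is correct for its formula. These are faults of consistency and accuracy in a confirmatory plan. They should be corrected, but they do not inflate type I error, and the power gap is small beside the uncertainty in the event rates.

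**What to change.** 1. **Align estimand and contrast** in Protocol 2.1.2 and 12.4.2 and in SAP 2.5.1 and 2.5.2. Either define the summary measure as the ratio of Day 29 cumulative proportions, or make the Kaplan-Meier risk difference with a Greenwood interval, adjusted for the interim, the primary contrast.
2. **Name the same test in the sizing text** (Protocol 12.8.1 and Table 12-2, SAP 3.1 and Table 3.1-2). Restate power as about 88% at 1717 and in the other seven rows, or about 88.5% if the risk difference is chosen. Say how the power was computed and what dropout is assumed.
3. **Decide explicitly about the 90% target.** Accepting 88% needs no more patients. Keeping 90% for the log-ratio test needs about 1,826 in total, 109 more than 1717, before any allowance for dropout.

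The first two changes cost only wording and a restated figure. They need a protocol amendment as well as the promised SAP amendment, and both should be in place before the first Part B patient.
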